### 11.3 Other Response Parameters

Additional response criteria for specific disease states:

Minor response in patients with relapsed and refractory myeloma adapted from the EMBT criteria 	$\geq 25\%$ but $< 49\%$ reduction of serum M protein and reduction in 24 hour urine M protein by 50 – 89%, which still exceeds 200 mg/24hrs.
---	--

	
In addition to above; if present at baseline, 25-49% reduction in the size of soft tissue plasmacytomas is also required
 
No increase in size or number of lytic bone lesions (development of compression fractures does not exclude response)

Immunophenotypic CR	Stringent CR plus Absence of phenotypic abarrent PC (clonal) in BM with a minimum of one million of total BM cells analyzed by miltiparamtric flow cytometry (with $\geq 4$ colors)
Molecular CR	Stringent CR plus negative ASO-PCR (sensitivity $10^{-5}$ )
Near Complete Response (adapted from the EMBT criteria  )	Patients, in whom all criteria for a CR are satisfied with exception of a positive or an unconfirmed immunofixation result, will be considered a near CR (nCR).

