
## 11 MEASUREMENT OF EFFECT

### 11.1 Antitumor Effect – Solid Tumors N/A

### 11.2 Antitumor Effect – Hematologic Tumors

#### 11.2.1 Methods for Evaluation of Measurable Disease

**Measurable disease.** Measurable disease is defined as at least one of the following (these baseline laboratory studies for determining eligibility must be obtained within 28 days prior to enrollment):

1. Serum M-protein  $\geq 0.5$  g/dl ( $\geq 5$  g/l)
2. Urine M-protein  $\geq 200$  mg/24 h
3. Serum free light chains (FLC) assay: Involved FLC level  $\geq 10$  mg/dl ( $\geq 100$  mg/l) and an abnormal serum free light chain ratio ( $< 0.26$  or  $> 1.65$ )
4. Biopsy proven plasmacytoma (should be measured within 28 days of first study drug administration). Prior biopsy is acceptable.
5. If the serum protein electrophoresis is unreliable for routine M-protein measurement, quantitative immunoglobulin levels on nephelometry or turbidometry will be followed.

Patients will be evaluated under local Investigator review for disease response according to the International Myeloma Working Group (IMWG) uniform response criteria (see 11.2.2; Rajkumar 2011).

Tests Required To Assess Response (Must Be Done At Each Disease Measurement Visit)				
On Study Baseline Value	SPEP	24 hr UPEP	Ig FLC	Plasmacytoma assessment
Serum M-spike $\geq 0.5$ g/dl, and urine M-spike $\geq 200$ mg/24 hrs	X	X		
Serum M-spike $\geq 0.5$ g/dl, but urine M-spike $< 200$ mg/24 hrs	X			
Serum M-spike $< 0.5$ g/dl, and urine M-spike $\geq 200$ mg/24 hrs		X		
Serum M-spike $< 0.5$ g/dl, urine M-spike $< 200$ mg/24 hrs, but involved Ig FLC is $\geq 10$ mg/dL			X	
Plasmacytoma				X a
Immunofixation studies of both serum and urine are required to document CR regardless of registration values, and in addition FLC measurement and BM immunophenotyping is required to document sCR. a Complete evaluations done at baseline with same technique Q 12 weeks.				

Listed above are the minimal required tests to assess response based on the characteristics of disease at study initiation. All baseline evaluations should be performed as closely as possible to the beginning of treatment and never more than 4 weeks before the beginning of the treatment.

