### 11.2.2 Response Criteria

International Myeloma Working Group Response Criteria (Rajkumar *et al.*, 2011)  
Response categories include sCR, CR, nCR, VGPR, PR, SD, and PD. In addition, minor response (MR) will be evaluated as an alternate response (see [Section 11.3](#) for definition).

Response	IMWG criteria
sCR	CR as defined below plus: 
 
• normal FLC ratio and
 
• absence of clonal cells in bone BM by immunohistochemistry or 2 – 4 color flow cytometry
 

CR	
 
• Negative immunofixation on the serum and urine and
 
• disappearance of any soft tissue plasmacytomas and
 
• < 5% plasma cells in BM.
 
• In patients with only FLC disease, a normal FLC ratio of 0.26–1.65 is required.
 

VGPR	
 
• Serum and urine M-protein detectable by immunofixation but not on electrophoresis or
 
• <math>\geq 90\%</math> reduction in serum M-protein plus urine M-protein level < 100 mg/24 h.
 
• In patients with only FLC disease, >90% decrease in the difference between involved and uninvolved FLC levels is required.
 

PR	
 
1. 50% reduction of serum M-protein and reduction in 24 hours urinary M-protein by <math>\geq 90\%</math> or to < 200 mg/24 h
 
 
 
• If the serum and urine M-protein are unmeasurable, a <math>\geq 50\%</math> decrease in the
 

	
difference between involved and uninvolved FLC levels is required in place of the M-protein criteria
 
 
• If serum and urine M-protein are not measurable, and serum free light assay is also not measurable, <math>\geq 50\%</math> reduction in plasma cells is required in place of M-protein, provided baseline BM plasma cell percentage was <math>\geq 30\%</math>
 
• In addition to the above listed criteria, if present at baseline, a <math>\geq 50\%</math> reduction in the size of soft tissue plasmacytomas is also required
 

Stable Disease	2. Not meeting criteria for CR, VGPR, PR or progressive disease

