**The primary objective is** to evaluate the antitumor activity of trametinib determined by overall response rate (ORR), in groups of patients with relapse or refractory multiple myeloma that are:

- Biomarker positive (NRAS, KRAS, BRAF mutated as defined [Appendix F](#))
- Biomarker negative (without NRAS, KRAS, BRAF mutation)

The endpoint for the primary objective, ORR, is evidenced by confirmed response rate, defined as number of patients with partial response or better by IMWG criteria divided by the number of patients in the applicable group (biomarker positive or negative). All patients included in the study will be assessed for response to treatment, even if there are major protocol treatment deviations or if they are ineligible (see section 13.5.2). The patient will be classified as having had a response if he/she has a confirmed response per the definitions in section [11.2.2](#). (i.e., a stringent complete response, or complete response or near complete response or very good partial response or partial response noted as the objective status of two consecutive assessments). The rate of minor response (MR) and progressive disease (PD) will also be observed.

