### 13.5.2 Evaluation of Response

All patients included in the study will be assessed for response to treatment, even if there are major protocol treatment deviations or if they are ineligible. Each patient will be assigned one of the following categories: 1) stringent complete response, 2) complete response, 3) very good partial response 4) partial response, 5) minimal response 6) stable disease, 7) progressive disease, 8) early death from malignant disease, 9) early death from toxicity, 10) early death because of other cause, or 11) unknown (not assessable, insufficient data).

All of the patients who met the eligibility criteria (with the possible exception of those who received no study medication) will be included in the main analysis of the response rate. Patients in response categories 7-10 should be considered to have a treatment failure (disease progression). Thus, an incorrect treatment schedule or drug administration does not result in exclusion from the analysis of the response rate.

All conclusions on treatment efficacy will be based on all eligible patients. Sub-analyses for objective response rate will be performed on all patients meeting the eligibility criteria, who have signed a consent form, and have begun study drug treatment, and had at least one follow-up assessment or progressive disease. This analysis will clearly report the reason for exclusion that may be based on major protocol deviations such as early death due to other reasons, early discontinuation of treatment, major protocol violations, etc. Further, the 95% confidence intervals will be provided.

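### Applied as written, the minor-response rule in 11.3 needs baseline urine M-protein above 400 mg/24 h, so serum-only and FLC-only patients, among others, cannot be scored MR and the descriptive MR rate is undercounted

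*Combined protocol and SAP*

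**What the plan says.** - **MR rule.** Section 11.3 asks for a serum M-protein fall of at least 25% but less than 49% *and* a "reduction in 24 hour urine M protein by 50 – 89%, which still exceeds 200 mg/24hrs". Conditions on plasmacytomas and bone lesions come on top. Nothing is substituted for patients who are not measurable in both serum and urine.
- **Status of MR.** Section 11.2.2 says that "minor response (MR) will be evaluated as an alternate response". Section 13.1 adds: "The rate of minor response (MR) and progressive disease (PD) will also be observed". Section 13.5.2 gives each patient one category from a list that includes "5) minimal response 6) stable disease, 7) progressive disease". I take minimal response there to be the MR of 11.3.
- **Disease patterns.** The table in 11.2.1 sets the tests by baseline disease. Patients with "Serum M-spike $\geq 0.5$ g/dl, but urine M-spike $< 200$ mg/24 hrs" need SPEP only. Those with "Serum M-spike $< 0.5$ g/dl, and urine M-spike $\geq 200$ mg/24 hrs" need 24-hour UPEP only. Those below both limits with involved FLC of at least 10 mg/dL need FLC only. Patients measurable in both need SPEP and UPEP. The text beneath states: "Listed above are the minimal required tests to assess response based on the characteristics of disease at study initiation".
- **PR and SD.** In 11.2.2, PR needs a 50% serum reduction and a urine reduction of at least 90% or to under 200 mg/24 h. An FLC criterion, then a marrow criterion, replaces these where M-protein is not measurable. SD is "Not meeting criteria for CR, VGPR, PR or progressive disease".

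**The concern.** The PR rule lets a patient with little urinary protein satisfy the urine limb, because urine under 200 mg/24 h counts as met. The MR rule turns that inequality round: urine must stay above 200 mg/24 h after falling by at least half. A patient who never had that much urinary protein cannot meet it, whatever the serum does. For serum-only patients the rule also depends on a urine measurement that 11.2.1 does not require.

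What is at stake is a descriptive rate. MR is the only category between PR and SD. If it is closed to some disease patterns, the reported MR rate depends partly on urinary burden at entry, and SD absorbs the difference. Response is judged by local investigators at several centres, so sites may also resolve the wording differently.

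**Working it through.** The plan states no expected MR rate or threshold, so there is no figure to reproduce. The check applies the rule to each row of the 11.2.1 table.

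**1. Baseline urine that the rule needs.** Let U be baseline urine M-protein (mg/24 h) and f the fractional fall, with f from 0.50 to 0.89. The rule needs U × (1 − f) > 200, that is, U > 200/(1 − f).

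| Fall f | Baseline needed |
|---|---|
| 50% | above 400 |
| 60% | above 500 |
| 75% | above 800 |
| 89% | above 1,818 |

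No patient with U of 400 or less can qualify.

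**2. The rule by disease pattern.**
- *Serum-only* (U < 200): after a 50% fall, urine is below 100. MR is impossible.
- *FLC-only* (U < 200): impossible for the same reason, and MR has no FLC limb.
- *Urine-only, no serum spike:* there is no serum value to fall by 25%. MR is impossible.
- *Urine-only, spike below 0.5 g/dL:* MR is possible. Serum 0.40 to 0.28 g/dL is a fall of 0.12/0.40 = 30%. Urine 1,000 to 400 is a fall of 60% that leaves 400, above 200.
- *Both measurable, U of 200–400:* impossible by step 1. Take serum 2.0 to 1.3 g/dL (0.7/2.0 = 35%) and urine 390 to 180 (210/390 = 54%). Urine is now under 200, so this is not MR; serum has not halved, so it is not PR.
- *Both measurable, U above 400:* possible. The same serum fall with urine 1,000 to 400 is MR. At U = 1,000, though, the fall must stay under 80%, since 1,000 × 0.20 = 200. A better urine result loses the category.

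**3. Gap between MR and PR.** MR stops below a 49% serum fall and PR starts at 50%. A fall of 49% to under 50% is neither.

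**4. Overlap of MR and SD.** The SD definition omits MR, so every MR patient also meets SD, while 13.5.2 assigns one category.

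**5. Size.** Understatement of the overall MR rate = (share of patients affected) × (their true MR rate). The documents give neither. As a pure assumption, take a share of 10–100% and a rate of 10–20%: 0.10 × 0.10 = 1 percentage point, and 1.00 × 0.20 = 20 percentage points. In a full group of 37 that is 0.37 to 7.4 patients. The range is too wide to serve as an estimate.

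**6. Primary design.** ORR counts PR or better. The rule in 13.2 (continue with at least 1 response in 12, accept with at least 4 in 37) gives P(accept) = Σ over x = 1 to 12 of Bin(x; 12, p) × P(Bin(25, p) ≥ max(0, 4 − x)). This is 0.0935 at p = 0.05 and 0.9024 at p = 0.20, against a stated 10% level and 90% power. MR appears nowhere in it.

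**The case against.** The strongest reply is that MR was meant to be scored on whichever component was measurable at baseline. Three places point that way. The 11.2.1 table requires SPEP alone for serum-only and UPEP alone for urine-only patients. The text after it speaks of urine and FLC as primary determinants of response. The notes to 11.2.2 single out VGPR and CR as needing both serum and urine studies whatever was measurable at baseline, which suggests that lower categories do not. The PR row also joins serum and urine by *and*; read just as strictly, it would bar urine-only patients without a serum spike from PR, which can hardly be intended.

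Much of this stands. On that reading, serum-only and urine-only patients can be MR. But these passages govern required tests and confirmation; none amends the MR criterion. The reading also leaves gaps. FLC-only patients still have no MR rule, patients measurable in both compartments with urine of 200–400 mg/24 h still cannot qualify, and the 49–50% gap and the overlap with SD remain. The last two are small: the gap is one percentage point wide and falls to SD by default, and the order of the list in 13.5.2 suggests that MR takes precedence.

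A reader might go further and infer any of the following; the documents do not support them.
- *No single-compartment patient can ever be MR.* The urine-only example with a small serum spike disproves this.
- *The reported rate is certain to be wrong.* That depends on how investigators apply the wording.
- *The efficacy conclusion or treatment decisions are affected.* MR is in no listed objective, and its rate has no test or threshold. The option to add GSK2141795 after four cycles applies to anything short of PR, so MR and SD are treated alike.
- *The comparison of biomarker groups is biased.* No between-group comparison of MR is planned.

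**Conclusion.** The point holds for the rule as written. Section 11.3 makes MR unattainable for all serum-only and FLC-only patients, for urine-only patients without a detectable serum spike, and for patients measurable in both compartments with baseline urine of 200–400 mg/24 h. If sites apply it literally, the error runs one way: MR is undercounted and SD overcounted. The amount cannot be derived, because it depends on the disease-pattern mix, the true MR rate and site practice. If sites score by component instead, the loss shrinks to FLC-only patients and the 200–400 mg/24 h group, but that practice has no stated basis for MR. The finding concerns a descriptive rate and is of low severity.

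**What to change.** Before analysis, change the wording of 11.3 and 11.2.2:

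1. In 11.3, apply the serum limb and the urine limb only to a component that was measurable at baseline under the 11.2.1 table.
2. Where serum is measurable and its fall is short of PR, do not disqualify a patient because urine drops below 200 mg/24 h.
3. Set the upper serum bound for MR at under 50%, so that it meets PR.
4. State whether FLC-only patients are scored by an FLC criterion taken from the source that the sponsor adapted, or are reported as not evaluable for MR. The documents contain no FLC threshold for MR, so none is proposed here.
5. In 11.2.2, define SD as not meeting CR, VGPR, PR, MR or PD, and use one name for MR in 11.3 and 13.5.2.

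The cost is wording only. Footnote c of the Study Calendar already schedules SPEP, FLC and 24-hour urine at baseline and before each cycle, while allowing that not every test is needed each time. Component-wise scoring needs only the tests that 11.2.1 already requires for each patient. Responses scored before the change can be reclassified from recorded values.

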## 12 DATA REPORTING / REGULATORY REQUIREMENTS

Adverse event lists, guidelines, and instructions for AE reporting can be found in Section 7.0 (Adverse Events: List and Reporting Requirements).

### 12.1 Data Reporting

#### 12.1.1 Method

This study will be monitored by the Clinical Data Update System (CDUS) Version 3.0. Cumulative protocol- and patient-specific CDUS data will be submitted electronically to CTEP on a quarterly basis, either by FTP burst of data or via the CDS web application. Reports are due January 31, April 30, July 31, and October 31. Instructions for submitting data using the CDUS can be found on the CTEP Web site (<http://ctep.cancer.gov/reporting/cdus.html>).

**Note:** If your study has been assigned to CDUS-Complete reporting, **all** adverse events (both routine and expedited) that have occurred on the study and meet the mandatory CDUS reporting guidelines must be reported via the monitoring method identified above. If your study has been assigned to CDUS-Abbreviated reporting, no adverse event reporting (routine or expedited) is required to be reported via CDUS.

### 12.1.2 Responsibility for Data Submission

Study participants are responsible for entering their data into the Medidata Rave system and submitting copies of their source notes to the Central Office / Coordinating Centre within 3 weeks of the end of cycle. Please refer to APPENDIX D DATA MANAGEMENT GUIDELINES, Data Management Guidelines, for further details regarding data submission requirements.

The Central Office / Coordinating Centre is responsible for compiling and submitting CDUS data to CTEP for all participants and for providing the data to the Principal Investigator for review.

## 12.2 CTEP Multicenter Guidelines

This protocol will adhere to the policies and requirements of the CTEP Multicenter Guidelines. The specific responsibilities of the Principal Investigator and the Coordinating Center (Study Coordinator) and the procedures for auditing are presented in APPENDIX B CTEP MULTICENTER GUIDELINES

- The Principal Investigator/Coordinating Center is responsible for distributing all IND Action Letters or Safety Reports received from CTEP to all participating institutions for submission to their individual IRBs for action as required.
- Except in very unusual circumstances, each participating institution will order DCTD-supplied agents directly from CTEP. Agents may be ordered by a participating site only after the initial IRB approval for the site has been forwarded by the Coordinating Center to the CTEP PIO ([contact]) except for Group studies.

## 12.3 Collaborative Agreements Language

The agent(s) supplied by CTEP, DCTD, NCI used in this protocol is/are provided to the NCI under a Collaborative Agreement (CRADA, CTA, CSA) between the Pharmaceutical Company(ies) (hereinafter referred to as “Collaborator(s)”) and the NCI Division of Cancer Treatment and Diagnosis. Therefore, the following obligations/guidelines, in addition to the provisions in the “Intellectual Property Option to Collaborator” ([http://ctep.cancer.gov/industryCollaborations2/intellectual\\_property.htm](http://ctep.cancer.gov/industryCollaborations2/intellectual_property.htm)) contained within the terms of award, apply to the use of the Agent(s) in this study:

1. Agent(s) may not be used for any purpose outside the scope of this protocol, nor can Agent(s) be transferred or licensed to any party not participating in the clinical study. Collaborator(s) data for Agent(s) are confidential and proprietary to Collaborator(s) and shall be maintained as such by the investigators. The protocol documents for studies utilizing Agents contain confidential information and should not be shared or distributed without the permission of the NCI. If a copy of this protocol is requested by a patient or patient’s family member participating on the study, the individual should sign a confidentiality agreement. A suitable model agreement can be downloaded from: <http://ctep.cancer.gov>.

2. For a clinical protocol where there is an investigational Agent used in combination with (an) other Agent(s), each the subject of different Collaborative Agreements, the access to and use of data by each Collaborator shall be as follows (data pertaining to such combination use shall hereinafter be referred to as "Multi-Party Data"):
  - a. NCI will provide all Collaborators with prior written notice regarding the existence and nature of any agreements governing their collaboration with NCI, the design of the proposed combination protocol, and the existence of any obligations that would tend to restrict NCI's participation in the proposed combination protocol.
  - b. Each Collaborator shall agree to permit use of the Multi-Party Data from the clinical trial by any other Collaborator solely to the extent necessary to allow said other Collaborator to develop, obtain regulatory approval or commercialize its own Agent.
  - c. Any Collaborator having the right to use the Multi-Party Data from these trials must agree in writing prior to the commencement of the trials that it will use the Multi-Party Data solely for development, regulatory approval, and commercialization of its own Agent.
3. Clinical Trial Data and Results and Raw Data developed under a Collaborative Agreement will be made available to Collaborator(s), the NCI, and the FDA, as appropriate and unless additional disclosure is required by law or court order as described in the IP Option to Collaborator ([http://ctep.cancer.gov/industryCollaborations2/intellectual\\_property.htm](http://ctep.cancer.gov/industryCollaborations2/intellectual_property.htm)). Additionally, all Clinical Data and Results and Raw Data will be collected, used and disclosed consistent with all applicable federal statutes and regulations for the protection of human subjects, including, if applicable, the *Standards for Privacy of Individually Identifiable Health Information* set forth in 45 C.F.R. Part 164.
4. When a Collaborator wishes to initiate a data request, the request should first be sent to the NCI, who will then notify the appropriate investigators (Group Chair for Cooperative Group studies, or PI for other studies) of Collaborator's wish to contact them.
5. Any data provided to Collaborator(s) for Phase 3 studies must be in accordance with the guidelines and policies of the responsible Data Monitoring Committee (DMC), if there is a DMC for this clinical trial.
6. Any manuscripts reporting the results of this clinical trial must be provided to CTEP by the Group office for Cooperative Group studies or by the principal investigator for non-Cooperative Group studies for immediate delivery to Collaborator(s) for advisory review and comment prior to submission for publication. Collaborator(s) will have 30 days from the date of receipt for review. Collaborator shall have the right to request that publication be delayed for up to an additional 30 days in order to ensure that Collaborator's confidential and proprietary data, in addition to Collaborator(s)'s intellectual property rights, are protected. Copies of abstracts must be provided to CTEP for forwarding to Collaborator(s) for courtesy review as soon as possible and preferably at least three (3) days prior to submission, but in

any case, prior to presentation at the meeting or publication in the proceedings. Press releases and other media presentations must also be forwarded to CTEP prior to release. Copies of any manuscript, abstract and/or press release/ media presentation should be sent to:

Email: [[contact]](mailto:[contact])

The Regulatory Affairs Branch will then distribute them to Collaborator(s). No publication, manuscript or other form of public disclosure shall contain any of Collaborator's confidential/proprietary information.

